9.4.4 Safety Analyses

No statistical analysis will be performed on safety endpoints. The Columbia Suicidality Rating Scale will be monitored at each visit. Any concerning result will trigger appropriate referral for mental health counseling or medical care.

Protocol 843748-
GET VIRTUAL PD
IMAGINE-PD

9.4.5 Baseline Descriptive Statistics

Counseling groups will be compared on baseline characteristics, including MoCA, Age, Sex, Disease Duration, vitals, and all secondary endpoint measurements. Parametric or nonparametric tests will be used to compare means or frequencies within groups.

9.4.6 Planned Interim Analyses

NA

9.4.7 Sub-Group Analyses

All Primary and Secondary endpoints will be compared using age and sex as covariates in each multivariate model. PD and Gene groups will also be compared.

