4 STUDY PLAN

4.1 Study Design

The proposed study is a single-center, prospective, factorial, non-inferiority, randomized cohort design to test the equivalence of telephone genetic counseling model to novel forms of pre-test genetic counseling and telegenetic results disclosure in participants with PD carrying a *GBA* or *LRRK2* variant (PD+*gene*+), participants with PD not carrying a *GBA* or *LRRK2* variant (PD+*gene*+), participants with PD not carrying a *GBA* or *LRRK2* variant (PD+*gene*-), and a group of at-risk *LRRK2* or *GBA* variant carriers without PD (PD-*gene*+). Participants will be recruited from a single center at the University of Pennsylvania Parkinson's Disease and Movement Disorders Center. A separate biobanking protocol, called the Molecular Inegration in Neurological Diagnosis MIND Cohort (UPenn IRB # 830237) enrolls subjects with PD and collects optional consent for recontact based on eligibility for additional studies. Subjects would be recruited to GET Virtual PD after enrolling MIND and after a blood or saliva sample has been collected and research-based genetic testing has been performed, but before clinical-confirmation genetic testing. GET Virtual PD will serve as the follow study to MIND that will allow access to genetic counseling and clinical genetic confirmation testing.

Enrolled participants will be randomized into one of 4 groups based on pre- and postgenetic test counseling: (1)IMAGINE-PD/Virtual, (2)IMAGINE-PD/Telephone, (3)Virtual/Virtual, and (4)Virtual/Telephone, stratified by genetic group. They will receive pretest genetic counseling through the Interactive Multimedia Approach to Genetic counseling to INform and Educate in Parkinson's Disease (IMAGINE-PD) website or via virtual visit with a genetic counselor. Participants will be asked to complete questionnaires on genetic knowledge, cognitive and affective outcomes prior to and 4 weeks after pre-test genetic counseling. All participants will then have clinical genetics results disclosure via virtual visit or by telephone with a genetic counselor. Patient-reported cognitive and affective outcomes will be measured 6 weeks and 6 months after genetic results disclosure. The hypothesis is that performance on the genetic knowledge scale and the revised impact of events scale will be equivalent between counseling groups at 4 weeks after pretest counseling and 6 weeks post disclosure, respectively.

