9.2 Sample Size Determination

The difference in IES-R between groups after genetic disclosure counseling is used to determine sample size. A clinically significant difference in IES-R score is not defined. Sample size is determined from previously reported normative data of the IES-R in a community sample of N=154 non-PTSD ex-service members, demonstrating a mean of 1.82 (SD=1.05).¹⁶ A range of equivalence limits, the difference in standard deviation beyond which a significant difference would be considered relevant, are demonstrated in **Table 3** at alpha = 0.05 and power of 80%.²⁵ A sample size of N=80/counseling group (divided between PD+gene+ (45%), PD+gene- (45%), and

PD-gene+ groups (10%)), with an expected attrition of 15-20%, would allow for analysis of the primary outcome at a conservative 0.5-0.75 SD equivalence limit, and allow genetic and PD-subgroup analysis.

8		8
Equivalence limit (SD)	Per Group	Total Sample Size
0.5	80	320
0.75	36	132
1	20	80

Table 3. Sample Size Estimates.

9.3 **Populations for Analyses**

Analyses will be conducted for all randomized participants *in the* Intention-to-Treat (ITT) Analysis Dataset, as well as the Per-Protocol Analysis Dataset defined a subset of the participants in the full analysis (ITT) set who complied with the protocol sufficiently to ensure that these data would be likely to represent the effects of study intervention according to the underlying scientific model (e.g., participants who complete the 3-month study visit).

Protocol 843748-
GET VIRTUAL PD
IMAGINE-PD

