9.4 Statistical Analyses

9.4.1 General Approach

Descriptive statistics will be presented as percentages for binary variables, and as means with standard deviations or median with IQR depending on the distribution of the data. For inferential tests, the Type I error will be set at 0.05 using two-tailed tests. Covariates will be determined based on their significance as independent predictors of outcome, although age and sex will be included in all models. Check on normality will be performed through data visualization as well as using appropriate statistical tests of normality (eg Shapiro-Wilks test). Transformation of non-normally distributed continuous variables will be performed, and models will be compared to non-transformed models using non-parametric tests.

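### Genetic group stratifies randomisation but is not a prespecified model term, and section 9.4.7 does not specify a counselling-mode contrast within variant carriers

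*Combined protocol and SAP*

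**What the plan says.** Section 4.1 describes testing equivalence in three kinds of participant: PD with a variant, PD without one, and variant carriers without PD. Allocation to the four counselling groups is "stratified by genetic group". Section 9.2 divides each group of 80 into 45%, 45% and 10% of these types and says the sample will serve the primary outcome "and allow genetic and PD-subgroup analysis".

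Section 9.4.7 has two sentences. The first is "All Primary and Secondary endpoints will be compared using age and sex as covariates in each multivariate model", which is covariate adjustment. The second is "PD and Gene groups will also be compared". It names no outcome contrast, model term or limit.

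The primary and secondary models in sections 9.4.2 and 9.4.3 adjust for age, sex and whatever other covariates are judged relevant. Section 9.4.1 makes entry of covariates other than age and sex depend on whether they prove significant predictors of the outcome.

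**The concern.** There are two gaps.

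First, a stratification factor is known before any outcome is seen. Leaving it to a significance rule makes the content of the primary model depend on the data, and it could differ between endpoints.

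Second, comparing carriers with non-carriers estimates the effect of the genetic result. It does not show whether video and telephone disclosure, or the website and a virtual visit, give similar outcomes among carriers. The IES-R is used here to measure test-related distress after disclosure, and 45% of participants carry no *GBA* or *LRRK2* variant. If mode mattered only to people told they carry a variant, the pooled difference would be diluted, and no analysis now written down would separate the groups.

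**Working it through.** **1. Wording.** In section 9.4.5, "Counseling groups will be compared on baseline characteristics" clearly means the named groups against one another. The second sentence of 9.4.7 has the same construction, so its plain reading is genetic group against genetic group. Sections 9.1 to 9.4.7 contain no mode contrast within a genetic group, no mode-by-group term and no sub-group limit.

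**2. The plan's own sample size.** Table 3 gives 80 per group at a 0.5 SD limit, "at alpha = 0.05 and power of 80"%. In SD units, with a true difference of 0 (assumed), two one-sided tests at 0.05 need n = 2 × ((1.645 + 1.282)/0.5)² = 68.5, so 69. Allowing 15% dropout gives 69 × 1.15 = 79.4, so 80 (or 69/0.85 = 81.2, so 82). A one-sided 0.025 non-inferiority calculation gives 63, and 63/0.80 = 78.75, so 79. The figure reproduces as a size for the overall counselling contrast, not for a sub-group.

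**3. Carriers per mode.** Two cells share each mode: 2 × 80 = 160. Carriers are 45% + 10% = 55%, so 0.55 × 160 = 88. After attrition, 88 × 0.80 = 70.4 and 88 × 0.85 = 74.8, so 70-75. Non-carriers are 0.45 × 160 = 72, or 58-61 after attrition.

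**4. Power for equivalence in carriers at 0.5 SD.** Power = 2Φ(0.5/√(2/n) − z) − 1, true difference 0.

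| n per mode | 0.5/√(2/n) | One-sided 0.05 | One-sided 0.025 |
|---|---|---|---|
| 70 | 2.958 | 81.1% | 68.2% |
| 75 | 3.062 | 84.4% | 73.0% |

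Exact t calculations give 81-84% and 67-72%. If single cells were compared instead of the two modes, 35-37 carriers per cell would give 33-37% at one-sided 0.05.

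**5. Dilution example (an assumption, not a document figure).** With a mode effect of 0.5 SD in carriers and 0 in non-carriers, the pooled effect is 0.55 × 0.5 = 0.275 SD. With 128-136 per mode after attrition, the standard error √(2/n) is 0.125-0.121. The chance of declaring pooled equivalence at 0.5 SD, one-sided 0.05, is Φ((0.5 − 0.275)/SE − 1.645): Φ(0.155) = 56% to Φ(0.210) = 58%. At one-sided 0.025 it is about 43-46%. At the 0.75 SD limit that section 9.2 also entertains, it is 98-99% at one-sided 0.05.

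**6. Interaction in the same example.** SE = √(2/70.4 + 2/57.6) = 0.251 at 20% attrition and √(2/74.8 + 2/61.2) = 0.244 at 15%. Two-sided 0.05 power is Φ(0.5/0.251 − 1.96) = 51% to Φ(0.5/0.244 − 1.96) = 54%.

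**7. Carriers without PD.** 0.10 × 160 = 16 per mode, 13-14 after attrition. The 90% interval half-width is 1.645 × √(2/13) = 0.645 to 1.645 × √(2/14) = 0.622 SD (0.64-0.67 with t), which is wider than a 0.5 SD limit.

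**The case against.** The sentence in 9.4.7 is terse and sits under a sub-group heading, after a sentence about comparing all endpoints. Sections 9.4.2 and 9.4.3 define those comparisons as between counselling groups, so it could mean repeating the counselling comparison within each genetic group. Sections 4.1 and 9.2 fit that reading. A reader might infer that the plan replaces the within-group contrast and therefore cannot show equivalence in carriers. The documents do not support that as fact: the intention is unclear, and the stratified data could support the analysis. What stands is that, on either reading, the contrast, model and limit are unwritten.

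A reader might also infer that genetic group is left out of the models and precision thereby lost. It is not excluded. If it predicts the IES-R strongly, the significance rule would tend to admit it. What stands is that its inclusion is not fixed in advance.

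The dilution argument has no source in the documents. Section 2.3.1 treats the risks of genetic testing as relevant to all participants, and even in the assumed case pooled equivalence at 0.5 SD would be declared only a little more than half the time.

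The carrier power also depends on the error rate. Section 9.4.1 states "For inferential tests, the Type I error will be set at 0.05 using two-tailed tests", and section 9.4.2 adds Bonferroni correction. Dividing by three primary endpoints (an assumption) lowers carrier power to about 59-65% starting from one-sided 0.05, or 43-50% from 0.025. Finally, section 9.1 makes no carrier-specific equivalence claim, so this contrast is supplementary.

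**Conclusion.** The point holds as one of incomplete specification. The randomisation stratum is not a prespecified term in any model, and the sub-group analysis that section 9.2 says the sample allows is not given a form that bears on counselling mode. It is worth correcting before analysis, but it does not undermine the primary comparison.

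For pooled carriers the main obstacle is the missing analysis. Power at 0.5 SD after attrition is 81-84% at one-sided 0.05, or about 68-73% at one-sided 0.025, resting on a true difference of 0, unit SD and the marginal factorial contrast. The interaction test is too weak to carry the conclusion, and carriers without PD are too few for any equivalence statement. It would go too far to say that the trial will hide a difference in carriers. The 0.275 SD pooled effect is illustrative and depends on non-carriers being unaffected by mode, which the documents do not establish.

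**What to change.** - In sections 9.4.2 and 9.4.3, include genetic group (three strata) as a fixed, prespecified factor in every primary and secondary model, exempt from the significance rule in 9.4.1.
- In section 9.4.7, replace the second sentence with an estimate of the counselling-mode difference and its confidence interval, given separately for carriers and non-carriers and for each factor of the design. Use the same confidence level and equivalence limit as the primary equivalence analysis. Both must first be settled, since section 9.2 gives a range of limits.
- Report the mode-by-carrier interaction as supportive only, and results for carriers without PD as descriptive.
- If a comparison of genetic groups with each other is also wanted, list it separately as a different question.

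The cost is SAP wording. The strata and outcome data are already planned, and no extra participants or visits are needed.

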9.4.8 Tabulation of Individual Participant Data

NA

10 SUPPORTING DOCUMENTATION AND OPERATIONAL CONSIDERATIONS

10.1 Regulatory, Ethical, and Study Oversight Considerations

10.1.1 Informed Consent Process

10.1.1.1 Consent/Assent and Other Informational Documents Provided To Participants

Consent forms describing in detail the study intervention, study procedures, and risks are given to the participant in electronic form and documentation of informed consent is required prior to starting intervention/administering study intervention via electronic consent.

10.1.1.2 Consent Procedures and Documentation

Informed consent is a process that is initiated prior to the individual's agreeing to participate in the study and continues throughout the individual's study participation. Consent forms will be Institutional Review Board (IRB)-approved and the participant will be asked to read and review the document. The investigator will explain the research study to the participant and answer any questions that may arise. A verbal explanation will be provided in terms suited to the participant's comprehension of the purposes, procedures, and potential risks of the study and of their rights as research participants. Participants will have the opportunity to carefully review the written consent form and ask questions prior to signing. The participants should have the opportunity to discuss the study with their family or surrogates or think about it prior to agreeing to participate. The participant will sign the informed consent document prior to any procedures

Page 34 of 41

being done specifically for the study. Participants must be informed that participation is voluntary and that they may withdraw from the study at any time, without prejudice. A copy of the informed consent document will be given to the participants for their records. The informed consent process will be conducted and documented in the source document (including the date), and the form signed, before the participant undergoes any study-specific procedures. The rights and welfare of the participants will be protected by emphasizing to them that the quality of their medical care will not be adversely affected if they decline to participate in this study.

10.1.2 Study Discontinuation and Closure

This study may be temporarily suspended or prematurely terminated if there is sufficient reasonable cause. Written notification, documenting the reason for study suspension or termination, will be provided by the suspending or terminating party to study participants. If the study is prematurely terminated or suspended, the Principal Investigator (PI) will promptly inform study participants, the Institutional Review Board (IRB), and sponsor and will provide the reason(s) for the termination or suspension. Study participants will be contacted, as applicable, and be informed of changes to study visit schedule.

Circumstances that may warrant termination or suspension include, but are not limited to:

- Determination of unexpected, significant, or unacceptable risk to participants
- Demonstration of efficacy that would warrant stopping
- Insufficient compliance to protocol requirements
- Data that are not sufficiently complete and/or evaluable
- Determination that the primary endpoint has been met
- Determination of futility

Study may resume once concerns about safety, protocol compliance, and data quality are addressed.

10.1.3 Confidentiality and Privacy

Participant confidentiality and privacy is strictly held in trust by the participating investigators, their staff, and the sponsor(s) and their interventions. This confidentiality is extended to cover testing of biological samples and genetic tests in addition to the clinical information relating to participants. Therefore, the study protocol, documentation, data, and all other information generated will be held in strict confidence. No information concerning the study or the data will be released to any unauthorized third party without prior written approval of the sponsor.

All research activities will be conducted in as private a setting as possible.

Representatives of the Institutional Review Board (IRB) or regulatory agencies may inspect all documents and records required to be maintained by the investigator, including but not limited

Protocol 843748-	
GET VIRTUAL PD	
IMAGINE-PD	

to, medical records (office, clinic, or hospital) and pharmacy records for the participants in this study. The clinical study site will permit access to such records.

The study participant's contact information will be securely stored at each clinical site for internal use during the study. At the end of the study, all records will continue to be kept in a secure location for as long a period as dictated by the reviewing IRB or Institutional policies.

Study participant research data, which is for purposes of statistical analysis and scientific reporting, will be kept in REDCap and transmitted to a local, secure database.

For participants who have clinical testing at Fulgent Genetics, their information including their name, date of birth, and genetic status will be shared with Fulgent and may be stored in the internal laboratory database during and after the conclusion of the study. This follows the standard-of-care for clinical genetic testing. After the study, Fulgent Genetics will not release information without the participant's express written consent, as specified by HIPAA guidelines and CLIA certification guidelines.

10.1.4 Future Use of Stored Specimens and Data

Fulgent Genetics may store the sample and data in an internal laboratory database as is the standard-of-care for clinical genetic testing. Fulgent Genetics will not perform additional analyses of the data without the express written consent of the participant and/or their physician. Fulgent Genetics may perform additional studies on the specimen collected for medical research and/or education, after it is anonymized, unless the participant contacts the lab directly to refuse and withdraw this consent.

10.1.5 Safety Oversight

Safety oversight will be under the direction of a Safety Monitor (SM) composed of an individual with the appropriate expertise, including movement disorders neurology or neurogenetics. The ISM should be independent from the study conduct and free of conflict of interest, or measures should be in place to minimize perceived conflict of interest. The SM will receive reports of safety data in the event of an AD or SAE.

10.1.6 Clinical Monitoring

Clinical site monitoring is conducted to ensure that the rights and well-being of trial participants are protected, that the reported trial data are accurate, complete, and verifiable, and that the conduct of the trial is in compliance with the currently approved protocol/amendment(s), with International Conference on Harmonisation Good Clinical Practice (ICH GCP), and with applicable regulatory requirement(s).

• The PI and Co-PI will conduct monitoring, on a yearly basis through a targeted review of certain data.

Protocol 843748–	
GET VIRTUAL PD	
IMAGINE-PD	Page 36 of 41

10.1.7 Quality Assurance and Quality Control

Quality control (QC) procedures will be implemented beginning with the data entry system and data QC checks that will be run on the database will be generated. Any missing data or data anomalies will be analyzed by the Investigator.

10.1.8 Data Handling and Record Keeping

10.1.8.1 Data Collection and Management Responsibilities

Data collection is the responsibility of the clinical trial staff under the supervision of the site investigator. The investigator is responsible for ensuring the accuracy, completeness, legibility, and timeliness of the data reported.

All source documents should be completed in a neat, legible manner to ensure accurate interpretation of data. Data will be recorded in the electronic case report form (eCRF) derived from source documents.

Clinical data (including adverse events (AEs), concomitant medications, and expected adverse events) and clinical laboratory data will be entered into REDCAP, a 21 CFR Part 11-compliant data capture system. The data system includes password protection and internal quality checks, such as automatic range checks, to identify data that appear inconsistent, incomplete, or inaccurate. Clinical data will be entered directly into REDCap.

Genetic data will be recorded in REDCAP for the study, and externally in the Fulgent Genetics internal laboratory database. The participants' data will be stored at Fulgent with the same management guidelines used for standard-of-care in clinical genetic testing.

10.1.8.2 Study Records Retention

Study documents should be retained for a minimum of 2 years after the formal discontinuation of clinical development of the study intervention. These documents should be retained for a longer period, however, if required by local regulations.

10.1.9 Protocol Deviations

A protocol deviation is any noncompliance with the clinical trial protocol, International Conference on Harmonisation Good Clinical Practice (ICH GCP), or protocol requirements. The noncompliance may be either on the part of the participant, the investigator, or the study site staff. As a result of deviations, corrective actions are to be developed by the site and implemented promptly.

These practices are consistent with ICH GCP:

Protocol 843748-
GET VIRTUAL PD
IMAGINE-PD

- 4.5 Compliance with Protocol, sections 4.5.1, 4.5.2, and 4.5.3
- 5.1 Quality Assurance and Quality Control, section 5.1.1
- 5.20 Noncompliance, sections 5.20.1, and 5.20.2.

It is the responsibility of the site investigator to use continuous vigilance to identify and report deviations within 10 working days of identification of the protocol deviation. All deviations must be addressed in study source documents, reported to IRB, per their policies. The site investigator is responsible for knowing and adhering to the reviewing IRB requirements.

10.1.10 Publication and Data Sharing Policy

This study will be conducted in accordance with the following publication and data sharing policies and regulations:

National Institutes of Health (NIH) Public Access Policy, which ensures that the public has access to the published results of NIH funded research. It requires scientists to submit final peer-reviewed journal manuscripts that arise from NIH funds to the digital archive PubMed Central upon acceptance for publication.

This study will comply with the NIH Data Sharing Policy and Policy on the Dissemination of NIH-Funded Clinical Trial Information and the Clinical Trials Registration and Results Information Submission rule. As such, this trial will be registered at ClinicalTrials.gov, and results information from this trial will be submitted to ClinicalTrials.gov. In addition, every attempt will be made to publish results in peer-reviewed journals. Data from this study may be requested from other researchers up to 10 years after the completion of the primary endpoint by contacting the Investigator

In addition, this study will comply with the NIH Genomic Data Sharing Policy, which applies to all NIH-funded research that generates large-scale human or non-human genomic data, as well as the use of these data for subsequent research. Large-scale data include genome-wide association studies (GWAS), single nucleotide polymorphisms (SNP) arrays, and genome sequence, transcriptomic, epigenomic, and gene expression data.

